7.3 Assessment of Baseline Conditions

In the efficacy analysis set, a frequency distribution will be shown for IGA (2 or 3) at baseline, and descriptive statistics will be shown for the total EASI (Eczema Area and Severity Index) score at baseline. Affected area at baseline will be classified into the following categories, and a frequency distribution will be shown.

Categories of affected area: \geq 5% and <10%, \geq 10% and <20%, \geq 20% and <40%, and \geq 40%

7.4 Treatment Compliance

In the efficacy analysis set, compliance regarding administration frequency until 52 weeks after baseline will be classified into the following categories, and the number and percentage of subjects will be calculated. In addition, the number and percentage of treated subjects will be calculated by week (Week 1, Week 2, Week 4, Week 8, Week 12, Week 16, Week 20, Week 24, Week 28, Week 32, Week 36, Week 40, Week 44, Week 48, Week 52, and Any Exposure). Compliance regarding administration frequency will be calculated using the following equation. Treatment compliance with IMP (%) = (Actual administration frequency / directed administration frequency of the 0.3% or 1% formulation) × 100

Categories of compliance regarding administration frequency: <50%, $\ge50\%$ and <60%, $\ge60\%$ and <70%, $\ge70\%$ and <80%, $\ge80\%$ and <90%, $\ge90\%$ and <100%, $\ge100\%$ and <110%, $\ge110\%$ and <120%, and $\ge120\%$

In addition, frequency distribution will be shown for the reasons for dose increase, dose reduction, and treatment interruption. If there are multiple reasons, the first reason will be counted.

7.5 Prior and Concomitant Medications

In the efficacy analysis set, the number and percentage of subjects receiving drugs will be calculated for drugs administered prior to the start day of IMP administration, drugs administered during the IMP administration period, and drugs administered after the end of IMP administration. Drugs will be coded by using the WHO Drug Dictionary and summarized by using ATC classification level 2 and Preferred names. Concomitant therapies will not be summarized but only listed.

7.6 Protocol Deviations

The number and percentage of subjects with a significant deviation from the protocol will be shown. In addition, the number and percentage of subjects by significant deviation category will be shown for each site.

8 Efficacy Analyses

The following analyses will be performed in the efficacy analysis set. In analyses of the primary endpoint, summarization will be performed for each of the following treatment groups: subjects secondly receiving only the 0.3% formulation even at 4 weeks postdose and later (hereinafter, the 0.3% formulation group) and subjects receiving the 1% formulation at least once at 4 weeks postdose or later (hereinafter, the 1% formulation

[dose increase] group). Unless otherwise noted, regardless of administration status (administration of the 0.3% formulation, administration of the 1% formulation, or treatment interruption), the data of the analysis time points specified in Table 3.4-1 will be summarized.

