Secondary objectives: This trial will be conducted in infants younger than 2 years of age with AD To investigate the safety of 0.3% OPA-15406 ointment when administered twice daily for 4 weeks To investigate the efficacy and safety of 0.3% or 1% OPA-15406 ointment when administered twice daily for 52 weeks To investigate the pharmacokinetics of 0.3% or 1% OPA-15406 ointment when administered twice daily for 4 weeks	 Efficacy endpoints: Response rate in Eczema Area and Severity Index (EASI) 90 (improvement of ≥90% in EASI), EASI 75 (improvement of ≥75% in EASI) and EASI 50 (improvement of ≥50% in EASI) Change from baseline in IGA score Percent change from baseline in the total score of EASI and each clinical sign score Change from baseline in the total score of Patient-Oriented Eczema Measure (POEM) Change from baseline in the total affected body surface area (BSA) (%) Safety endpoints: Adverse events (AEs) Vital signs, body weight Clinical laboratory tests Pharmacokinetic endpoint: Plasma concentration of OPA-15406 	

3 Trial Design

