3.2.2.3 Interruption (Treatment Interruption)

IMP administration must not be suspended until the Week 4 examination. Interruption will be allowed if judged necessary by the investigator or subinvestigator (eg, resolution of skin symptoms, exacerbation of skin symptoms [which requires rescue medication], occurrence of an AE [excluding exacerbation of skin symptoms]) at a 4-weekly

assessment after the Week 4 examination (in the long-term extension part). Interruption will be recorded together with the reason in the source documents and eCRF. The investigator or subinvestigator should perform the specified examination/assessments during interruption, and decide on the necessity of restarting IMP administration.

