3.2.2.4 Restarting IMP Administration After Interruption

Following interruption, restarting IMP administration (exacerbation of skin symptoms, improvement of skin symptoms [in cases where IMP administration was suspended to allow rescue medication], improvement of an AE [excluding exacerbation of skin symptoms]) will be recorded together with the reason in the source documents and eCRF.

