5.4 Handling of Missing Data

Missing data are not imputed. For IGA response, EASI 75, EASI 90, and EASI 50, subjects with missing IGA or EASI scores are handled as non-responders.

6 Primary and Secondary Endpoints

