8.2 Key Secondary Efficacy Endpoint Analyses

In the same manner as the primary endpoint analysis in 8.1, the number of subjects with an IGA response and success rate at each assessment time point and their two-sided 95% confidence intervals (Clopper-Pearson method) will be calculated for each treatment group and all subjects.

By using OC data, the number of subjects with an IGA response and success rate at each assessment time point and the last time (Last Visit) and their two-sided 95% confidence intervals (Clopper-Pearson method) will be calculated for each treatment group and all subjects. The success rate at each assessment time point will be graphically shown.

The cumulative number and rate of subjects who improved at least once by each assessment time point with IGA response and their two-sided 95% confidence intervals (Clopper-Pearson method) will be calculated by treatment group and for all subjects. The success rate at each assessment time point will be graphically shown.

EASI 75, EASI 90, and EASI 50 will be analyzed in the same manner as IGA response.

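### The Week 8 to Week 52 by-visit and cumulative IGA and EASI response rates count successes scored under or after rescue as responses, and no analysis in the public text counts them as non-response

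*Combined protocol and SAP*

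**What the plan says.** The secondary objectives in SAP section 2 include this one: "To investigate the efficacy and safety of 0.3% or 1% OPA-15406 ointment when administered twice daily for 52 weeks".

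Section 8 states that, unless otherwise noted, data at the Table 3.4-1 time points are summarised "regardless of administration status (administration of the 0.3% formulation, administration of the 1% formulation, or treatment interruption".

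The responder rules are in sections 3.5.1, 3.5.2, 5.4 and 8.1. A subject is a non-responder if the criterion is not met or the score is missing. Section 5.4 puts the second part as follows: "For IGA response, EASI 75, EASI 90, and EASI 50, subjects with missing IGA or EASI scores are handled as non-responders". None of these sections mentions rescue.

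Section 3.2.2.3 allows interruption after Week 4, and its example reasons include "exacerbation of skin symptoms [which requires rescue medication". It adds: "The investigator or subinvestigator should perform the specified examination/assessments during interruption". Section 3.2.2.4 names among the reasons for restarting "improvement of skin symptoms [in cases where IMP administration was suspended to allow rescue medication".

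Section 8.2 reports the IGA response in three forms: by visit with missing scores as non-response, by visit on observed cases (OC), and cumulatively. The last is described as "The cumulative number and rate of subjects who improved at least once by each assessment time point with IGA response". EASI 50, 75 and 90 are handled in the same way.

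Section 8.4 splits response by use of listed topical anti-inflammatory drugs at any time in the administration period. It does so at Week 4 and Last Visit. Week 52 as such is split only by age.

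**The concern.** The long-term objective concerns the efficacy of OPA-15406, yet the plan expects that some infants will stop it for a flare, receive rescue and go on being assessed. If such an infant's score meets the criterion, the tables credit a response. The trial is open-label and uncontrolled, so no between-group contrast can take out the contribution of rescue.

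The cumulative rate is the most exposed form, because one qualifying score under rescue is enough to count the infant as improved from then on. A reader of the 52-week tables could not tell how much of the reported response was scored under rescue.

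**Working it through.** The plan states no figure on this point, so there is none to reproduce. The check sets the rules side by side and then bounds the effect.

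**1. How a post-rescue score is classified**

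- *During an interruption for rescue:* explicit. Section 8 includes interruption visits, section 3.2.2.3 keeps the assessments going, and section 3.5.1 looks only at the score.
- *After topical anti-inflammatory use without interruption:* inferred. No section sets such a score to missing or to non-response. The only data that section 3.4 excludes from the time points are certain unscheduled records around the increase to 1%.

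Example: an infant has baseline IGA 3, IMP is suspended for rescue, and IGA is 1 at Week 24 during the suspension. The improvement is 3 - 1 = 2 grades, so the criterion is met. The infant is a responder at Week 24 in CT-5.1.2 and CT-5.1.3. If this is the first success, the infant also counts in CT-5.1.4 from Week 24 to Week 52. Improvement under rescue need not reach the criterion. The point concerns only scores that do.

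**2. Direction**

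Counting flagged scores as non-response, with the denominator unchanged, can only remove responders. The planned rates are therefore equal to or higher than the alternative at each of the (52 - 8)/4 + 1 = 12 time points from Week 8 to Week 52.

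**3. Size per visit (all inputs assumed)**

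Let q be the share of infants on or just after rescue at a visit, and s the share of those whose score meets the criterion. Excess = q x s.

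| q | s | Excess (points) |
|---|---|---|
| 5% | 25% | 0.05 x 0.25 = 1.25 |
| 5% | 50% | 0.05 x 0.50 = 2.5 |
| 10% | 25% | 0.10 x 0.25 = 2.5 |
| 10% | 50% | 0.10 x 0.50 = 5.0 |

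For scale, assume N = 40 and 28 responders: 70.0% (Clopper-Pearson 95% CI 53.5 to 83.4). An excess of 5.0 points is 0.05 x 40 = 2 infants, and 26/40 is 65.0% (48.3 to 79.4).

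**4. Size of the cumulative excess**

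Only an infant with a flagged success and no unflagged success by that time point adds to the excess. It therefore cannot exceed the share of infants ever rescued. A narrower range would need the number of flagged visits per infant and the dependence between visits, and the documents give neither.

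**5. What the visible plan already gives**

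- CT-6.1.7, 6.2.7, 6.3.7 and 6.4.7 split response by anti-inflammatory use at Week 4 and Last Visit. Responders in the absent stratum, divided by all subjects, give a conservative bound at those two points. For completers, Last Visit will normally be the Week 52 record.
- The size of the present stratum, divided by all subjects, caps the excess from topical use in every rate with an all-subject denominator.
- CT-7.3.3 gives reasons for interruption and CT-4.2 gives drugs taken during treatment.

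None of these links rescue to response at a given visit. The stratum is defined by any use, not by timing relative to the visit. Subject listings (EFF-1, EFF-2, PDATA-4.2, PDATA-17) may hold the pieces, but no table listed in Appendix 2 assembles them.

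**The case against.** The strongest reply is that this is a choice between estimands and not an error. The SAP states in advance that data are used whatever the administration status. The affected rates are descriptive secondary results, and the visible text sets no test, comparator or success threshold for them. With no control arm, a rate that counts rescue as non-response would not isolate the drug effect either. All of this stands. It is why the planned analysis should stay and why the addition is supplementary.

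The planned tables will also show how common rescue was and will cap the effect of topical use. That stands too. What they lack is the visit-level figure.

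The public text is incomplete on this point. Section 8.5 shows only its heading, and the protocol's own rescue and withdrawal rules are not visible. Section 8.4 calls the listed drugs prohibited. If their use leads to withdrawal, few post-rescue visits may exist. Absence is therefore claimed for the public text only.

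A reader might infer that the long-term rates are invalid or heavily inflated. The documents do not support that: they fix the direction but not the size. A reader might also extend the point to the Week 4 primary endpoint, or take that endpoint to be untouched. Neither follows. Section 3.2.2.3 bars interruption before Week 4 but does not address topical anti-inflammatory use, and section 8.4 plans a Week 4 split by such use.

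**Conclusion.** The point holds as a gap in the supporting analyses. For interruption visits the counting rule is explicit. For rescue without interruption it is inferred from the absence of any rescue term. Relative to counting rescue as non-response, the Week 8 to Week 52 rates can only be equal or higher.

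The amount is unknown. The range of 1.25 to 5.0 points per visit rests wholly on the assumed q and s, and for the cumulative rate only the ceiling can be stated. Confidence is medium. The priority is that of a low-cost supplementary analysis of descriptive secondary endpoints.

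**What to change.** Keep the planned analyses. Add to section 8.2 one supplementary analysis of the by-visit, OC and cumulative rates for IGA response and EASI 50, 75 and 90. In it, the adopted assessment counts as non-response, stays in the denominator and does not count towards the cumulative rate, if either condition holds:

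- (a) it was made while IMP was interrupted for rescue; or
- (b) a topical anti-inflammatory drug listed in section 8.4 was used at any time from the assessment adopted for the preceding analysis time point up to the date of the assessment adopted for this one.

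The look-back in (b) runs between adopted assessments because section 3.4 lets unscheduled and withdrawal records fill a window and takes the last value. A look-back to the previous scheduled visit would miss rescue given just before that visit when a later unscheduled score in the same window is adopted. Interruption because symptoms resolved is unaffected. Fix the rule before database lock. It changes the analysis only and proposes no rule for rescue or interruption.

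Cost: SAP wording, one derived visit-level flag, and up to 3 x 4 = 12 extra tables. The reason for interruption should be available: "Interruption will be recorded together with the reason in the source documents and eCRF". Section 8.4 already needs drug use. Condition (b) also assumes usable medication dates, which cannot be confirmed from the public text.

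Downsides: the added rates may be lower than the planned ones. The look-back is a convention that penalises brief use early in an interval and ignores later carry-over. Systemic rescue without interruption is not captured.

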8.1 Primary Efficacy Endpoint Analysis

Response (improvement) is defined as a postdose IGA score of 0 or 1 with improvement of at least 2 grades, and the primary endpoint is the success rate in IGA at Week 4. In all subjects of the efficacy analysis set, the number of subjects with an IGA response and success rate at 4 weeks after IMP treatment and their two-sided 95% confidence intervals (Clopper-Pearson method) will be calculated. The same analysis will be performed at 1 week and 2 weeks postdose. Subjects with missing IGA data will be handled as non-responders. The success rate at each assessment time point will be graphically shown.

8.2 Key Secondary Efficacy Endpoint Analyses

In the same manner as the primary endpoint analysis in 8.1, the number of subjects with an IGA response and success rate at each assessment time point and their two-sided 95% confidence intervals (Clopper-Pearson method) will be calculated for each treatment group and all subjects.

By using OC data, the number of subjects with an IGA response and success rate at each assessment time point and the last time (Last Visit) and their two-sided 95% confidence intervals (Clopper-Pearson method) will be calculated for each treatment group and all subjects. The success rate at each assessment time point will be graphically shown.

The cumulative number and rate of subjects who improved at least once by each assessment time point with IGA response and their two-sided 95% confidence intervals (Clopper-Pearson method) will be calculated by treatment group and for all subjects. The success rate at each assessment time point will be graphically shown.

EASI 75, EASI 90, and EASI 50 will be analyzed in the same manner as IGA response.

8.3 Secondary Efficacy Endpoint Analysis

Regarding IGA score, total EASI score, EASI score of each symptom and each part, total POEM score, and total affected area (%), the descriptive statistics of actual measurements and changes from baseline at each assessment time point and the last time (Last Visit) will be calculated for each treatment group and all subjects. For the IGA score, total EASI score, EASI score of each symptom and each part, and total POEM score, the descriptive statistics will be calculated for percent change from baseline as well. For

Protocol 271-102-00016

changes in IGA from baseline, the time courses of changes in IGA score from baseline at each timepoint will be plotted with the mean and SD. As for total EASI score, the time courses of changes in total EASI score from baseline at each timepoint will be plotted with the mean and SD.

Regarding IGA score, by using OC data, the shift table at each assessment time point and the last time (Last Visit) from baseline will be shown for each treatment group and all subjects.

8.5 Exploratory or Other Analyses

9 Safety Analysis

In the safety analysis set, the following analyses will be performed. Unless otherwise noted, the summarizations described below will be performed for each of the following treatment groups and for all subjects: subjects receiving only the 0.3% formulation even at 4 weeks postdose and later (hereinafter referred to as the 0.3% formulation group) and subjects receiving the 1% formulation at least once at 4 weeks postdose or later (hereinafter, the 1% formulation [dose increase] group).

9.1 Extent of Exposure to Investigational Medicinal Product

Descriptive statistics will be calculated for the number of days of administration (except for treatment interruption), total amount of IMP administration, and amount of administration per dose. The amount of administration is defined as the difference between the total weights of prescribed IMP and returned IMP. In addition, descriptive statistics will also be shown in the same manner for the amount with consideration of IMP concentration (0.3% OPA-15406 and 1% OPA-15406). In calculating the amount of treatment, the weight of the IMP with an unknown weight upon return will be calculated as 0 (zero) at return.

The sum of treatment duration and the descriptive statistics of treatment duration for 0.3% OPA-15406, and the sum of treatment duration and the descriptive statistics of treatment duration for 1% OPA-15406 will be calculated. The same analysis will be performed for age categories (<12 months, \ge 12 months). Furthermore, for subjects aged <12 months, the same analysis will be performed by the following categories: <6 months and \ge 6 and <12 months.

9.2 Adverse Events

By using MedDRA (Ver 26.1), adverse events will be coded by system organ class (SOC) and preferred term (PT).

Regarding the following treatment-emergent AEs (TEAEs), the number and percentage of subjects with an onset will be calculated. If the same event occurred multiple times in the same subject, the most severe one will be used in analyses by severity, and the one with the earliest onset will be used in analyses by onset time. For skin and subcutaneous tissue disorders, analyses by the grade classification of the Common Terminology Criteria for Adverse Events (CTCAE) will also be performed.

- TEAE
- TEAEs by severity
- TEAEs with an outcome of death
- Serious TEAEs
- TEAEs leading to discontinuation of the IMP
- TEAEs leading to IMP treatment interruption
- TEAEs leading to IMP dose reduction
- TEAEs by CTCAE Grade (only for skin and subcutaneous tissue disorders)
- TEAEs at treatment areas
- TEAEs by onset time (\leq 4 weeks, >4 and \leq 12 weeks, >12 and \leq 24 weeks, >24 and \leq 36 weeks, >36 and \leq 52 weeks, and >52 weeks)

Adverse reactions (adverse events whose relationships with the IMP cannot be ruled out) will be analyzed in the same manner as TEAEs.

Serious TEAEs, TEAEs leading to discontinuation of the IMP, TEAE leading to IMP treatment interruption, and TEAEs leading to IMP dose reduction will be summarized by severity and CTCAE Grade.

For TEAEs that developed in \geq 5% of any treatment group and non-serious TEAEs that developed in \geq 5% of any treatment group, the number and percentage of subjects with an onset will be calculated.

In addition, TEAEs will be summarized in regard to the following items.

- TEAEs except for events that developed during the treatment interruption period
- TEAEs that developed by 4 weeks after IMP administration (only for all subjects)
- TEAEs that developed by 8 weeks after IMP administration
- TEAEs that developed in the treatment area
- TEAEs that developed in the treatment area by 4 weeks after IMP administration

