3.1 Type/Design of Trial

This trial is a phase 3, multicenter, open-label, uncontrolled trial to evaluate the efficacy and safety of OPA-15406 ointment in infants younger than 2 years of age with atopic dermatitis.

1) Screening period

After obtaining informed consent from the subject's legal guardian, the investigator or subinvestigator will perform the screening examination. The screening period is defined as the period between the day of screening examination and the day of baseline examination (2 - 30 days).

2) IMP administration period

The IMP administration period is defined as the period between the day of baseline examination and the end of Week 52 examination (or the end of withdrawal examination). The primary assessment part is defined as the period between the baseline examination and the Week 4 examination, and the long-term extension part is defined as the period between the Week 4 examination and the Week 52 examination. Subjects who meet the inclusion and exclusion criteria at the baseline examination will be prescribed with the IMP. The IMP will be administered to the treatment area from the day of baseline examination twice daily for 52 weeks. If a subject discontinues the IMP administration between the day of baseline examination and the day of Week 52 examination, a withdrawal examination will be performed for that subject.

3) Trial period

The trial period for individual subjects is the period from the day of obtaining the written informed consent from the subject's legal guardian to the day of the Week 52 examination (or withdrawal examination). For subjects who missed the Week 52 examination (or withdrawal examination), the day of discontinuation will be the day when the investigator or subinvestigator determined that the subject was to be withdrawn from the trial. It does not include the follow-up period for AEs.

	Screening period (2 - 30 days)	IMP administration period (52 weeks)			IMF		
		OPA-15	assessment 0.3% 5406 ointm vice daily			[Long-term extension part] ^a 0.3% or 1% OPA-15406 ointment Twice daily	
Informed consent	Baseline examination	Week 1 examination	Week 2 examination	Week 4 examination	 •		Week 52 examination

a Long-term extension part (Week 4 - 52 examination)

- Subjects are scheduled to visit every 4 weeks, and the use of 1% formulation is also acceptable in accordance with dose increase criteria.

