- CT-8.2.2.7 Adverse Events According to Application Site (Between Baseline and Week 4) - Age: Greater Than or Equal to 6 Months (Subjects Under 12 Months of Age)
- CT-8.3.1 Adverse Events Occurring on Treatment
- CT-8.4.1.1 Treatment-emergent Adverse Events on Treatment by System Organ Class, Preferred Term and Period of Onset

- CT-8.4.1.2 Drug-related Treatment-emergent Adverse Events on Treatment by System Organ Class, Preferred Term and Period of Onset
- CT-8.4.1.3 Treatment-emergent Adverse Events on Treatment by System Organ Class, Preferred Term and Period of Onset (CTD Format)
- CT-8.5.1.1.1 Incidence of Treatment-emergent Adverse Events by System Organ Class and Preferred Term
- CT-8.5.1.1.2 Incidence of Treatment-emergent Adverse Events by System Organ Class and Preferred Term Sex: Male
- CT-8.5.1.1.3 Incidence of Treatment-emergent Adverse Events by System Organ Class and Preferred Term Sex: Female
- CT-8.5.1.1.4 Incidence of Treatment-emergent Adverse Events by System Organ Class and Preferred Term Age: Less Than 12 Months
- CT-8.5.1.1.5 Incidence of Treatment-emergent Adverse Events by System Organ Class and Preferred Term Age: Greater Than or Equal to 12 Months
- CT-8.5.1.1.6 Incidence of Treatment-emergent Adverse Events by System Organ Class and Preferred Term With Topical Anti-Inflammatory Agents
- CT-8.5.1.1.7 Incidence of Treatment-emergent Adverse Events by System Organ Class and Preferred Term Without Topical Anti-Inflammatory Agents
- CT-8.5.1.1.8 Incidence of Treatment-emergent Adverse Events by System Organ Class and Preferred Term With Topical Medications Excluding Anti-Inflammatory Agents
- CT-8.5.1.1.9 Incidence of Treatment-emergent Adverse Events by System Organ Class and Preferred Term Without Topical Medications Excluding Anti-Inflammatory Agents
- CT-8.5.1.1.10 Incidence of Treatment-emergent Adverse Events by System Organ Class and Preferred Term Onset Timing of Administration of 0.3% OPA-15406
- CT-8.5.1.1.11 Incidence of Treatment-emergent Adverse Events by System Organ Class and Preferred Term Onset Timing of Administration of 1% OPA-15406
- CT-8.5.1.1.12 Incidence of Treatment-emergent Adverse Events by System Organ Class and Preferred Term Age: Less Than 6 Months (Subjects Under 12 Months of Age)
- CT-8.5.1.1.13 Incidence of Treatment-emergent Adverse Events by System Organ Class and Preferred Term Age: Greater Than or Equal to 6 Months (Subjects Under 12 Months of Age)

- Protocol 271-102-00016

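### TEAE percentages by onset period cannot be compared across bands 4 to 16 weeks wide, because Section 9.2 plans no band denominator or time at risk

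*Combined protocol and SAP*

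**What the plan says.** SAP Section 9.2 sets one statistic for all the listed TEAE summaries: "Regarding the following treatment-emergent AEs (TEAEs), the number and percentage of subjects with an onset will be calculated". The list includes "TEAEs by onset time", with cut points at 4, 12, 24, 36 and 52 weeks and a final band for anything later. For repeat events in the same subject, "the one with the earliest onset will be used in analyses by onset time". Drug-related events are handled the same way.

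Appendix 2 plans three tables on this basis, CT-8.4.1.1 to CT-8.4.1.3. The first is titled "Treatment-emergent Adverse Events on Treatment by System Organ Class, Preferred Term and Period of Onset"; the second covers drug-related events and the third is in CTD format.

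Section 9.2 gives no denominator for a band, no time at risk and no rate. Section 9.1 sums treatment duration by concentration but does not link it to adverse events. Section 7.4 counts treated subjects at each scheduled week.

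On visits, Table 3.4-1 has Weeks 1, 2 and 4 in the primary assessment part. In the extension, Section 3.1 says "Subjects are scheduled to visit every 4 weeks", with one further visit 2 weeks after a first increase to 1%.

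**The concern.** A reader will look along the row of an onset-period table to see whether risk changes with duration of use. The last full band is four times as wide as the first, so it has about four times as long to collect first onsets of an uncommon event. The percentage can therefore grow while the risk stays level or falls.

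The trial is uncontrolled, so no comparator column would show the same artefact. These are also the only planned adverse event tables that divide the whole 52 weeks by time; the summaries to Week 4 and to Week 8 cover only the early period. What is at stake is the reading of long-term safety in infants, not the primary efficacy result.

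**Working it through.** **Inputs from the documents.** Band limits in weeks are 0, 4, 12, 24, 36 and 52 (Section 9.2). The widths are 4, 8, 12, 12 and 16, a ratio of 1 : 2 : 3 : 3 : 4. Only the first onset of an event counts. Scheduled visits per band are 3, 2, 3, 3 and 4, which is 3/4 = 0.75 per week in the first band and 0.25 per week afterwards.

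**Assumptions.** The documents show no expected event rate, withdrawal rate or band denominator, and so no figure to reproduce. I assume a constant hazard λ per week, all dosed subjects as denominator (the safety set of Section 5.2) and, at first, no withdrawal.

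**Step 1: constant hazard.** The percentage in the band from a to b is exp(−λa) − exp(−λb), where λ = −ln(1 − P)/52 and P is the 52-week incidence. For P = 10%, λ = 0.00203. The first band is 1 − exp(−4λ) = 0.81%, the last is exp(−36λ) − exp(−52λ) = 2.97%, and the ratio is 3.67.

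| P | 0–4 | >4–12 | >12–24 | >24–36 | >36–52 | last/first |
|---|---|---|---|---|---|---|
| 1% | 0.08 | 0.15 | 0.23 | 0.23 | 0.31 | 3.97 |
| 10% | 0.81 | 1.59 | 2.34 | 2.29 | 2.97 | 3.67 |
| 30% | 2.71 | 5.19 | 7.28 | 6.70 | 8.12 | 3.00 |
| 50% | 5.19 | 9.59 | 12.60 | 10.73 | 11.89 | 2.29 |
| 80% | 11.64 | 19.38 | 21.40 | 14.76 | 12.82 | 1.10 |
| 90% | 16.23 | 24.99 | 24.23 | 14.24 | 10.31 | 0.64 |

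The last band equals the first at P of about 82% and is smaller above that.

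**Step 2: withdrawal.** With withdrawal hazard d, the percentage is λ/(λ+d) × [exp(−(λ+d)a) − exp(−(λ+d)b)]. For an assumed 20% withdrawal by Week 52, d = −ln(0.8)/52. The last/first ratio falls to 3.31 at P = 1%, 3.07 at 10% and 1.91 at 50%.

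**Step 3: falling risk.** Take a hazard of 0.01 per week to Week 4 and 0.005 afterwards. The first band is 1 − exp(−0.04) = 3.9%. The last is exp(−0.04) × [exp(−0.16) − exp(−0.24)] = 6.3%. The full row is 3.9, 3.8, 5.4, 5.1 and 6.3%, so a halved risk shows as a 1.6-fold rise. With 20% withdrawal the row still goes from 3.9% to 5.2%.

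**Step 4: visit density.** If detection were wholly proportional to scheduled visits, a rare event with constant risk would show 3 : 2 : 3 : 3 : 4, or 1, 0.67, 1, 1 and 1.33 relative to the first band. This is an outer limit; it shows that denser early visits reduce the rise.

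**Step 5: does a rate remove the artefact?** Dividing first onsets by subject-time at risk, stopped at first onset, gives the same value in every band under constant hazard: 10.54 per 100 person-years at P = 10% and 69.31 at P = 50%. Dividing by band width alone does not: at P = 50%, 5.19/4 = 1.30 in the first band falls to 11.89/16 = 0.74 per 100 person-weeks in the last, a false decline.

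**The case against.** The best case for the plan is that these are descriptive counts in bands with stated limits. Section 9.2 announces no trend test and no claim about time. Treated-subject counts at every band boundary (Section 7.4) and summed durations (Section 9.1) give a careful reader some context. The separate summaries to Week 4, including the one for the treatment area, isolate early application reactions directly. This limits the harm, but none of it gives a rate per band, and side-by-side columns invite the comparison.

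Three stronger readings are tempting, and the documents do not support them:

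- **That percentages rise about 4-fold with time on drug as a general matter.** Four-fold is the limit for rare events. The ratio shrinks with commoner events and with withdrawal, and it reverses for very common ones, perhaps an any-TEAE row. Nor is the rise steady: the third and fourth bands are equally wide, so the fourth is level or lower.
- **That the three-fold visit density in the first 4 weeks adds to the rise.** It works against it. It is another reason the bands are not comparable, but how far visits drive detection is not shown in the documents.
- **That an event concentrated early would be hidden.** With assumed hazards of 0.01 and then 0.001 per week, the bands show 3.9, 0.8, 1.1, 1.1 and 1.5%, and the early peak is plain. Only a moderate decline, such as a halving, is turned into an apparent rise.

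**Conclusion.** The concern holds in a limited form. As planned, percentages by onset period are not comparable across bands. Width alone can make the last full band up to about 4 times the first for rare events, and a moderate fall in risk can appear as an increase. For any given event, the net distortion depends on its incidence, on withdrawal and on how far visits drive detection, none of which the documents state. The figures above rest on assumed hazards, an assumed 20% withdrawal where noted, and all dosed subjects as denominator. The tables are descriptive safety tables, so the change is worth making but does not bear on the validity of the primary result.

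**What to change.** In Section 9.2 and in CT-8.4.1.1 to CT-8.4.1.3:

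- State the denominator and show, for each band, the number of subjects still under observation.
- For each SOC and PT row and each treatment group, add the first-onset incidence rate per subject-time at risk. Time at risk comes from subjects with no earlier onset of that event and is censored at first onset or end of observation. It differs from row to row, so a single row of observation time will not do: common events would then show the false decline in Step 5.
- Base any statement about time trend on these rates, not on the percentages.
- Footnote the visit schedule: Weeks 1, 2 and 4, then 4-weekly, plus the visit 2 weeks after a first increase to 1%.
- Footnote the short coverage of the band after Week 52. In Table 3.4-1 the Week 52 window closes on Day 372, which is 372 − 7 × 52 = 8 days past Day 364.

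The cost is modest. The rates need only onset and observation dates, which the planned onset and exposure summaries already require. The three tables become larger, and rates will be imprecise where events are few.
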